11. INTERIM ANALYSIS

Not applicable.

12. IMMUNOGENICITY ANALYSIS

Analysis of immunogenicity data will be based on IGS. Analysis dataset and data listing will include all available Human Anti-Human Antibody (HAHA, ADA) samples. The following terms and definitions are implemented.

12.1. Terms and Definitions

12.1.1. Sample ADA Status:

- Baseline ADA-positive sample: ADA is detected in the last sample before initiation of treatment.
- Baseline ADA-negative sample: ADA is not detected in the last sample before initiation of treatment.
- **Treatment-emergent ADA-Positive:** Meets definition of treatment-induced or treatment-boosted ADA. After initiation of treatment,
 - **Treatment-induced ADA-Positive:** a post-treatment positive ADA is detected in a subject for whom pre-treatment ADA assessment is either negative or not assessable, or
 - **Treatment-boosted ADA-Positive:** pre-existing ADA were boosted to a higher level following study treatment, i.e. pre-treatment positive ADA titer was boosted by at least 2 dilution steps (4-fold) following study treatment.
- ADA-negative sample: After initiation of treatment, ADA is not ADA-positive sample relative to baseline.

Next, using the sample ADA status, subject ADA status is defined.

12.1.2. Subject ADA Status:

- Baseline ADA-positive subject: A subject with baseline ADA-positive sample.
- ADA-positive subject: An evaluable subject with at least one treatment-emergent ADA sample at any time during the study.
- Neutralizing-positive: At least one treatment-emergent ADA-positive sample with neutralizing antibodies detected (if available).
- ADA-negative subject: An evaluable patient without a treatment-emergent ADA-positive sample during the study.

12.2. Statistical Analysis for Characterization of ADA Immune Response

12.2.1. Incidence of ADA

- Percentage of treatment-emergent ADA patients for the defined study period, where the denominator is the number of ADA evaluable patients in the respective treatment arm and/or subgroup.
- Number (%) of subjects will be reported for the following parameters based on evaluable subjects:
 - Baseline ADA-positive
 - ADA-positive (Treatment-induced, Treatment-boosted)
 - Neutralizing Positive (if available)
 - ADA-negative
- ADA prevalence: Percentage of treatment-emergent ADA patients at any given timepoint, where the denominator is the number of ADA evaluable patients in the respective treatment arm and/or subgroup at that timepoint.
- A listing of all ADA assessments will be provided.
- Additionally, a separate listing of ADA assessments for all neutralizing antibody (NAb)-positive subjects will be provided (if available).

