12.2.2. ADA Titer Kinetics

All ADA-positive subjects will be included in the analysis.

- Summary statistics of subject-level ADA titers using the maximum titer value within an ADA positive subject will be presented for baseline ADA-negative subjects and baseline ADA positive subjects. The median, interquartile range, and range of the maximum titers will be reported. For ADA-positive subjects with baseline ADA-positive sample, the median and interquartile range of the fold increase from baseline in titer (ratio of maximum post-baseline titer to baseline titer) will also be reported. Graphical presentation of the summary data may be provided using boxplots, as appropriate.
- For sample-level ADA titers, boxplots of ADA titers at each assessment timepoint will be provided, as appropriate, to demonstrate whether the ADA levels tend to change over time during the treatment, along with ADA incidence at each assessment timepoint.
- Spider plots may be considered to show the trend of ADA titer over time for subjects with $>/= 5$ ADA results by splitting subjects into multiple spider plots (eg, $\approx \leq 10$ per plot, approximately).

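### The percentage labelled ADA prevalence counts treatment-emergent antibody only, so persistent baseline positives without a 4-fold titer rise are counted as negative

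*SAP*

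**What the plan says.** SAP 12.2.1 gives two percentages. The period measure is "Percentage of treatment-emergent ADA patients for the defined study period, where the denominator is the number of ADA evaluable patients". The timepoint measure, named ADA prevalence, is "Percentage of treatment-emergent ADA patients at any given timepoint, where the denominator is the number of ADA evaluable patients", restricted to those evaluable at that timepoint. Addendum 3.3.1 uses the same definitions for the main study.

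The numerator depends on SAP 12.1. Treatment-emergent positivity is described as "Meets definition of treatment-induced or treatment-boosted ADA", which gives two routes:

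- Treatment-induced: "a post-treatment positive ADA is detected in a subject for whom pre-treatment ADA assessment is either negative or not assessable".
- Treatment-boosted: "pre-treatment positive ADA titer was boosted by at least 2 dilution steps (4-fold) following study treatment".

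For samples taken after treatment starts, 12.1.1 also has "ADA-negative sample: After initiation of treatment, ADA is not ADA-positive sample relative to baseline". Addendum 3.2.1 states this more directly: a sample that is not treatment-emergent positive is negative. Both texts then class an evaluable subject with no treatment-emergent sample as ADA-negative.

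The Immunogenicity Analysis Set (SAP 5.2.2, Addendum 3.1) requires a reportable sample before and after treatment. It does not exclude subjects who are positive at baseline. Both texts also plan a row for baseline positives and a listing of all ADA assessments.

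**The concern.** A reader who finds prevalence next to incidence in an immunogenicity table will take prevalence as the share of subjects with antibody at that timepoint, whatever its origin. The planned figure leaves out one group: subjects with pre-existing antibody that persists without a 4-fold rise. Both percentages draw on the same numerator class, so the second adds a time axis to incidence and does not measure how many subjects carry antibody.

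The row for baseline positives does not fill the gap, because it does not show who is still positive later. The titer summaries do not fill it either: SAP 12.2.2 and Addendum 3.3.2 include only ADA-positive subjects, which by definition excludes this group. What is at stake is a descriptive percentage that may be too low, and that can read 0% while some subjects have detectable antibody.

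**Working it through.** The documents state no ADA count, rate or expected prevalence, so there is no planned figure to reproduce. The check is a reading of the definitions followed by count arithmetic.

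**Step 1: follow one subject through the rules.** Take a subject who is ADA-positive before treatment and ADA-positive afterwards, with a titer rise of less than 4-fold.

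| Rule | Result |
|---|---|
| Analysis set (SAP 5.2.2, Addendum 3.1) | Included: reportable samples before and after treatment |
| Treatment-induced | No: baseline was positive |
| Treatment-boosted | No: rise below 4-fold |
| Sample status after treatment | Negative, although antibody is detected |
| Subject status | ADA-negative |
| Prevalence numerator | Not counted |
| Prevalence denominator | Counted |

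**Step 2: write the two quantities.** At a timepoint, let k be the number of treatment-emergent subjects, b the number of persistent unboosted positives, and N the number evaluable.

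- Prevalence as planned: k/N
- Share with any ADA: (k + b)/N
- Gap: (k + b)/N − k/N = b/N

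The planned figure can never exceed the any-ADA share, and it is lower whenever b is at least 1.

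**Step 3: put in numbers.** N = 22 is the planned enrolment (Protocol synopsis), used here as the evaluable number. N = 15 and N = 10 are assumed, to allow for fewer evaluable subjects. All values of b are assumed.

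| N | b = 0 | b = 1 | b = 2 | b = 3 |
|---|---|---|---|---|
| 22 | 0 | 4.5 points | 9.1 | 13.6 |
| 15 | 0 | 6.7 | 13.3 | 20.0 |
| 10 | 0 | 10.0 | 20.0 | 30.0 |

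Example with assumed counts k = 1, b = 2, N = 22: the planned figure is 1/22 = 4.5%, and the any-ADA share is 3/22 = 13.6%.

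**Step 4: how likely is the case to arise?** The documents give no baseline-positive rate. For an assumed rate p, the chance of at least one baseline positive among N subjects is 1 − (1 − p)^N.

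| p | N = 22 | N = 10 |
|---|---|---|
| 2% | 36% | 18% |
| 5% | 68% | 40% |
| 10% | 90% | 65% |

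These are upper bounds on the chance that b is at least 1, because not every baseline positive will stay positive and unboosted.

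**Step 5: where the figure can be computed.** Protocol Appendix 5 schedules human anti-human antibody (HAHA) samples at Day 0 and at safety follow-up. The open-label extension (OLE) schedule in Protocol Appendix 6 has them at Day 0 and at Week 210/EOS/ET. Within each period, the only scheduled sample after Day 0 is therefore taken once dosing has ended.

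**The case against.** The best defence is that the SAP defines its term in full, numerator and denominator, under a heading about incidence. On that view a careful reader can see what is counted and only the label is in dispute. The definition is indeed stated openly. But a table carries the label and not the definition, and the label names a quantity that the table does not contain.

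Four further points on the other side stand, and they limit the concern:

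- **The information is not lost.** All ADA samples go into the dataset and the listing. With about 22 planned subjects and one scheduled follow-up sample per period, persistent positives can be found by hand. What is missing is a summary.
- **The figure does not describe infusion visits or exposure.** A reader might infer that the table misstates who carries antibody when infused. The schedule does not support this, because the post-treatment sample falls after the last dose. No drug level is scheduled alongside it: main-study PK sampling stops at Week 52, and the OLE schedule lists none.
- **Duplication is not proven.** SAP 12.2.2 asks for boxplots "along with ADA incidence at each assessment timepoint" but does not define that incidence, so it cannot be shown to be the same number.
- **Nothing is decided on it.** Immunogenicity is not a protocol objective or endpoint. The safety and efficacy explorations in Addendum 3.4 use ADA status, not prevalence.

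A reader might also infer that the OLE table hides antibody induced by the drug in the main study. That would follow only if the OLE baseline in SAP 5.4.3 governs section 12. Section 12 does not say which first dose starts treatment, so the documents leave this open. It is a separate question and the present point does not rest on it.

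**Conclusion.** The concern holds as a mislabelled descriptive summary. The definitions in both texts give treatment-emergent incidence by timepoint under the name prevalence, and no planned table reports the share of subjects with any ADA after baseline.

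The size is b/N. At 22 evaluable subjects that is 1/22, or about 4.5 points, for each persistent unboosted positive, and more if fewer subjects are evaluable. It is wrong to say that the reported figure will be too low: if no such subject exists, b is 0 and the two quantities agree. The definitional finding needs no assumption, but every numerical example rests on an assumed b, and those below 22 also on an assumed N.

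Efficacy conclusions are unaffected. This is a minor correction, worth making because it uses data already planned for collection.

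**What to change.** In SAP 12.2.1 and Addendum 3.3.1, define ADA prevalence at a timepoint as the number of subjects with any ADA-positive sample then, pre-existing or treatment-emergent, divided by the number with a reportable sample at that timepoint. Keep the existing treatment-emergent percentage and call it incidence, for the study period and by timepoint.

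The cost is one sentence in each text, one programming condition and a rerun of one descriptive table per period. No new samples are needed. The main-study part is less convenient: the Addendum was issued after database lock and the interim study report, so the change needs a further documented amendment and a table produced after lock.

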12.2.2. ADA Titer Kinetics

All ADA-positive subjects will be included in the analysis.

- Summary statistics of subject-level ADA titers using the maximum titer value within an ADA positive subject will be presented for baseline ADA-negative subjects and baseline ADA positive subjects. The median, interquartile range, and range of the maximum titers will be reported. For ADA-positive subjects with baseline ADA-positive sample, the median and interquartile range of the fold increase from baseline in titer (ratio of maximum post-baseline titer to baseline titer) will also be reported. Graphical presentation of the summary data may be provided using boxplots, as appropriate.
- For sample-level ADA titers, boxplots of ADA titers at each assessment timepoint will be provided, as appropriate, to demonstrate whether the ADA levels tend to change over time during the treatment, along with ADA incidence at each assessment timepoint.
- Spider plots may be considered to show the trend of ADA titer over time for subjects with $>/= 5$ ADA results by splitting subjects into multiple spider plots (eg, $\approx \leq 10$ per plot, approximately).

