3.3.2. ADA Titer Kinetics

All ADA-positive subjects will be included in the analysis.

- Summary statistics of subject-level ADA titers using the maximum titer value within an ADA positive subject will be presented for baseline ADA-negative subjects and baseline ADA positive subjects. The median, interquartile range, and range of the maximum titers will be reported. For ADA-positive subjects with baseline ADA-positive samples, the median and interquartile range of the fold increase from baseline in titer (ratio of maximum post-baseline titer to baseline titer) will also be reported. Graphical presentation of the summary data may be provided using boxplots, as appropriate.
- For sample-level ADA titers, boxplots of ADA titers at each assessment timepoint will be provided, as appropriate, to demonstrate whether the ADA levels tend to change over time during the treatment, along with ADA incidence at each assessment timepoint.
- Spider plots may be considered to show the trend of ADA titer over time for subjects with ≥ 5 ADA results by splitting subjects into multiple spider plots (e.g., ≈ 10 per plot, approximately).

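### The ADA fold-increase summary is restricted to subjects already defined by a rise of at least 4-fold, so it cannot fall below 4 and does not describe titer change in subjects with pre-existing ADA

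*SAP*

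**What the plan says.** SAP 12.2.2 opens with its population: "All ADA-positive subjects will be included in the analysis". Within it, the fold increase is summarised thus: "For ADA-positive subjects with baseline ADA-positive sample, the median and interquartile range of the fold increase from baseline in titer". The statistic is the "ratio of maximum post-baseline titer to baseline titer". Sample-level boxplots by timepoint are planned "to demonstrate whether the ADA levels tend to change over time during the treatment, along with ADA incidence at each assessment timepoint".

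The terms are fixed in SAP 12.1:
- An ADA-positive subject is "An evaluable subject with at least one treatment-emergent ADA sample at any time during the study".
- A sample is treatment-emergent if it is treatment-induced or treatment-boosted.
- Treatment-induced means "a post-treatment positive ADA is detected in a subject for whom pre-treatment ADA assessment is either negative or not assessable".
- Treatment-boosted means that the "pre-treatment positive ADA titer was boosted by at least 2 dilution steps (4-fold) following study treatment".

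The SAP Addendum, which covers the main study, repeats these definitions in 3.2 and the restriction in 3.3.2: "For ADA-positive subjects with baseline ADA-positive samples, the median and interquartile range of the fold increase from baseline in titer".

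SAP 12.2.1 and Addendum 3.3.1 also give counts of evaluable subjects who are baseline ADA-positive, ADA-positive (induced or boosted) and ADA-negative, together with a listing of every ADA assessment.

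**The concern.** A reader who sees a fold-increase row for baseline-positive subjects will probably take it as the typical titer change on treatment in people who already had antibody. As defined, the row is conditioned on the outcome it reports: a subject enters only if the titer rose at least 4-fold. Baseline-positive subjects whose titer stayed level, fell or rose 2-fold are absent from the only summary of titer change, and nothing on the row says so.

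The boxplots raise a related, weaker question. They are meant to show whether levels change over time, but the section's lead sentence appears to choose their subjects because those subjects had a treatment-emergent result.

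What is at stake is an overstated impression of how far pamrevlumab boosts pre-existing antibody. The primary endpoint is not touched.

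**Working it through.** **The plan's own figure.** Two dilution steps in a serial 2-fold dilution give 2² = 4, which matches the 4-fold stated in SAP 12.1.

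**The floor, from the definitions alone.**
1. The fold-increase subset is ADA-positive and baseline-positive (SAP 12.2.2).
2. ADA-positive requires at least one treatment-emergent sample (SAP 12.1.2).
3. The treatment-induced route needs a negative or non-assessable pre-treatment result, so it is closed to baseline-positive subjects (SAP 12.1.1).
4. Each subject in the subset therefore has some post-baseline titer of at least 4 × baseline.
5. Hence maximum post-baseline / baseline ≥ 4 for every subject, and the minimum, quartiles and median are all ≥ 4.

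No data or assumption enters these steps. Addendum 3.2 and 3.3.2 give the same result.

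**Size beyond the floor (assumptions, not in the documents).** Take baseline-positive subjects with no drug effect and a stable underlying titer (mean 4 steps, between-subject SD 1.5). Each measured titer varies with an SD of 1.0 or 1.5 two-fold steps and is rounded to whole steps. There are 1 to 3 post-baseline samples and 400,000 simulated subjects.

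| SD per titer (steps) | Post-baseline samples | Pass the 4-fold rule by chance | Median max/baseline, all baseline-positive | Q1 / median / Q3 in the SAP's subset |
|---|---|---|---|---|
| 1.0 | 1 | 14.7% | 1 | 4 / 4 / 8 |
| 1.0 | 2 | 23.7% | 2 | 4 / 4 / 8 |
| 1.0 | 3 | 30.1% | 2 | 4 / 4 / 8 |
| 1.5 | 1 | 23.7% | 1 | 4 / 4 / 8 |
| 1.5 | 2 | 36.4% | 2 | 4 / 8 / 8 |
| 1.5 | 3 | 44.6% | 2 | 4 / 8 / 16 |

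With no true change, the SAP's subset would report a median of 4 to 8. Over all baseline-positive subjects the median is 1 with one post-baseline sample. With two or three it is 2, because taking the maximum pushes the ratio up even without selection.

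**The plots.** One qualifying sample at any time makes a subject ADA-positive, while the boxplots use titers at every timepoint. A subject with titers 20 (baseline), 80, 10 qualifies (80/20 = 4), yet the plotted titer then falls to 10/20 = 0.5 of baseline. In the simulation, among selected subjects with 2 or 3 post-baseline samples:
- 44% to 76% show a fall between successive post-baseline samples;
- 12% to 36% have a post-baseline titer below baseline;
- 35% to 51% end below 4-fold.

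Only with a single post-baseline sample must each selected subject show a rise. That case is relevant here. Protocol Appendix 5 marks antibody sampling (HAHA) at Day 0 and safety follow-up in the main study, and the Appendix 6 schedule marks Day 0 and Week 210/EOS/ET in the OLE. Within either period that is one scheduled post-baseline sample. If the periods are combined there can be more, up to 4 scheduled results in all.

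**The case against.** The best defence is that the row describes responders: it gives the size of the rise among boosted subjects, names its subset, and the 4-fold threshold is defined a page earlier. No test or decision uses it, and the safety and efficacy explorations in Addendum 3.4 go by ADA status, not fold increase. Immunogenicity is not a listed objective or endpoint. In a study planned for about 22 subjects, few may be baseline-positive, and each can be read from the listing. All of this stands, and it keeps the point minor. It does not remove the floor, and it leaves titer change in non-boosted baseline-positive subjects without any summary.

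Two stronger readings are tempting, and the documents do not support them:
- *That the plots can show only increases.* The 20, 80, 10 example disproves this as a general statement. Moreover, the lead sentence says that ADA-positive subjects are included, not that others are excluded, and the spider-plot bullet sets its own condition (at least 5 results). The restriction of the boxplots is an inference.
- *That the plan cannot show how often pre-existing antibody was boosted.* SAP 12.2.1 and Addendum 3.3.1 report both the boosted and the baseline-positive counts, and their ratio is that proportion. Baseline-positive subjects who were not boosted remain in those tables as ADA-negative. What is missing is a summary of their titer change.

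**Conclusion.** The point holds for the fold-increase summary in both SAP 12.2.2 and Addendum 3.3.2. By definition it covers treatment-boosted subjects only, so its median and quartiles cannot be below 4, and it does not describe titer change in subjects with pre-existing ADA. This rests on the plan's wording alone.

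For the boxplots the conclusion is conditional. If the lead sentence restricts them to ADA-positive subjects, they over-represent rises. A rise is forced for every included subject only where there is a single post-baseline sample in the period analysed.

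The chance pass rates of 15% to 45% and the reported medians of 4 to 8 rest on an assumed titer SD of 1 to 1.5 steps and 1 to 3 samples. They illustrate the direction and are not estimates for this trial. The documents do not say how many subjects are baseline-positive. This is a minor correction to a descriptive summary, and it changes no efficacy or safety conclusion.

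**What to change.** In SAP 12.2.2 and Addendum 3.3.2:
- Report fold change from baseline for all evaluable baseline-ADA-positive subjects, including ratios of 1 or less. Give the treatment-boosted subset as a second line, labelled as such.
- Where a subject has more than one post-baseline sample, report last post-baseline / baseline next to maximum / baseline, because the maximum is biased upward. State how a negative post-baseline sample, which has no titer, enters the ratio.
- State that the over-time boxplots include every evaluable subject with any positive sample at baseline or later.

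The cost is a change of analysis population and one added ratio in two sections. No new samples are needed, because SAP 12 and Addendum 3.1 already place all available ADA samples in the analysis dataset. The downside is that the boosting figure becomes less striking.

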13. CHANGES FROM PROTOCOL

- The date of the first dose in the OLE period will be considered as the date of Day 1 for all analyses during the OLE period, instead of Day 0.
- Efficacy parameters, including change from baseline of the main study in ppFVC, PUL, grip strength, LVEF%, and cardiac MRIs including cardiac fibrosis score assessed by Late Gadolinium Enhancement (LGE), and Myocardial Circumferential Strain [Global Circumferential Strain (GCS)], will be analyzed at Week 48/52, Week 96/104, etc. in the OLE period using Mixed Model for Repeated Measures (MMRM) additionally.

15. APPENDICES

APPENDIX 1. ANALYSIS VISIT WINDOWS

Table 1: Assessment Windows for PFT

Analysis Visit	Window
Baseline	Value at the visit on or prior to the first dose of study drug Target day=1, window = $[L_0, H_0] = [-, 1]$
Week X	$X = 24*K$, $k=1, 2, \dots, 7$ Target day = $7 * X + 1$ Window = $[L_K, H_K] = [H_{K-1}+1, \text{Target Day}+24*7/2-1]$
Week 192	$[L_8 = H_7+1 = 1261, **]$

** There will be no upper bound; all assessments will be included.

Table 2: Assessment Windows for Muscle Function Tests

Analysis Visit	Window
Baseline	Value at the visit on or prior to the first dose of study drug Target day=1, window = $[L_0, H_0] = [-, 1]$
Week X	$X = 12*K$, $k=1, 2, \dots, 16$ Target day = $7 * X + 1$ Window = $[L_K, H_K] = [H_{K-1}+1, \text{Target Day}+12*7/2-1]$
Week 204	$[L_{17} = H_{16} +1=1387, **]$

** There will be no upper bound; all assessments will be included.

Table 3: Assessment Windows for Cardiac MRI

Analysis Visit	Window
Baseline	Value at the visit on or prior to the first dose of study drug Target day=1, window = $[L_0, H_0] = [-,1]$
Week X	$X = 52*K$, $k=1, 2, 3$ Target day = $7 * X + 1$ Window = $[L_K, H_K] = [H_{K-1}+1, \text{Target Day}+52*7/2-1]$
Week 208	$[L_4 = H_3+1= 1275, **]$

* There will be no upper bound; all assessments will be included.

Table 4: Assessment Windows for Vital Signs

Analysis Visit	Window
Baseline	Baseline are defined as the average of last Screening and Week 0 pre-infusion measurements. Target day=1, window = $[L_0, H_0] = [-,1]$
Week X	$X = 2*K$, $k=1, 2, 3, \dots, 105$ Target day = $7 * X + 1$ Window = $[L_K, H_K] = [H_{K-1}+1, \text{Target Day}+6]$

*The last visit window will not have an upper bound; all assessment will be included.

Table 5: Assessment Windows for Labs Tests

Analysis Visit	Window
Baseline	Value at the visit on or prior to the first dose of study drug Target day=1, window = $[L_0, H_0] = [-,1]$
Week X	$X = 24*K$, $k=1, 2, \dots, 8$ Target day = $7 * X + 1$ Window = $[L_K, H_K] = [H_{K-1}+1, \text{Target Day}+24*7/2-1]$
Week 210	$[L_9 = H_8+1= 1408, **]$

* There will be no upper bound; all assessments will be included.

All scheduled and unscheduled assessments are included in the by-visit summary. If more than two assessments are available in the same window, the last assessment will be used in the by- visit summary.

If any visit is missed, assessments should be performed as soon after the missed visit as feasible. Missed infusions will not be replaced.

Pamrevlumab infusion is NOT to be administered at week 208 (EOT).

